12.1 Study Drugs and Procedures

12.1.1 Pegylated Interferon Alpha 2b

Interferon alpha is a cytokine with proven antiviral activity against many viruses, especially HCV. The exact mechanism of this antiviral activity is not known. The proposed mechanisms of actions for interferon alpha are:

1. Antiviral activity through the inhibition of viral replication in infected cells (Sen 2001, Bekisz, Schmeisser et al. 2004, Jiang, Guo et al. 2008). With respect to HIV-1 specifically, INF has shown antiviral activity both *in vitro* (Ho, Hartshorn et al. 1985) and *in vivo* (Lane, Kovacs et al. 1988, Hatzakis, Gargalianos et al. 2001) studies.
2. Immune regulatory actions increasing the ability of reticuloendothelial cells to clear virus through the following mechanisms (Missale, Bertoni et al. 1996, Gerlach, Diepolder et al. 1999, Patel and McHutchison 2001):
 - a. Increase in class 1 MHC antigens and cellular adhesion molecules on effector cells
 - b. Activation of effector cells (NK cell and macrophages)
 - c. Upregulation of Th1-T helper subset

In participants with cirrhosis, exacerbation of cirrhosis-related neutropenia and thrombocytopenia is a recognized risk associated with interferon and pegylated interferon. Participants with documented cirrhosis will be excluded from

participating in this study. The other recognized side effects associated with the use of pegylated interferon include fatigue, headaches, myalgia, fever, nausea, upper abdominal discomfort, depression, diarrhea, insomnia, reduced appetite, and dermatitis. There are also rare occurrences of autoimmune, infections, ophthalmic, and ischemic disorders associated with pegylated interferon use. Ophthalmologic complications include retinopathy, which is usually transient and completely resolves with continued treatment. Other side effects associated with subcutaneous injection include pain and inflammation at the site of injection.

The specific adverse events listed below will be handled as specified. PEGINTRON will be administered in clinic by trained personnel. Merck Inc. will be providing study drug PEGINTRON; other study agents will be provided through respective pharmacies as indicated.

12.1.2 Granulocyte Colony Stimulating Factor

Endogenous granulocyte colony stimulating factor (G-CSF) is a lineage specific colony-stimulating factor, which is produced by monocytes, fibroblasts, and endothelial cells. G-CSF regulates the production of neutrophils within the bone marrow and affects neutrophil progenitor proliferation, differentiation, and selected end-cell functional activation.

Filgrastim is a human granulocyte colony-stimulating factor (G-CSF), produced by *Escherichia coli* bacteria into which has been inserted the human granulocyte colony-stimulating factor gene. Filgrastim is available as a sterile, clear, colorless, preservative-free liquid for parenteral administration at a specific activity of $1.0 \pm 0.6 \times 10^6$ U/mg (as measured by a cell mitogenesis assay). The product is available in single-use vials and prefilled syringes. The single-use vials contain either 300 µg or 480 µg filgrastim at a fill volume of 1.0 mL or 1.6 mL, respectively. It has been shown to be safe and effective in accelerating the recovery of neutrophil counts following a variety of chemotherapy regimens. Filgrastim is contraindicated in patients with known hypersensitivity to *E. coli*-derived proteins, or any component of the product. Allergic-type reactions occurring on initial or subsequent treatment have been reported in <1 in 4000 patients treated with filgrastim. These have generally been characterized by systemic symptoms involving at least 2 body systems, most often skin (rash, urticaria, facial edema), respiratory (wheezing, dyspnea), and cardiovascular (hypotension, tachycardia). Some reactions occurred on initial exposure. Reactions tended to occur within the first 30 minutes after administration IV. Rapid resolution of symptoms occurred in most cases after administration of antihistamines, steroids, bronchodilators, and/or epinephrine. Symptoms recurred in more than half the patients who were rechallenged. Other rarely reported serious complications associated with filgrastim include splenic rupture, acute respiratory distress syndrome, alveolar hemorrhage and hemoptysis, and sickle cell crises. G-CSF will be administered in clinic by trained personnel.

12.1.3 Potential for Previously Unrecognized Drug Interactions

Interferon alpha 2b has been co-administered with antiretroviral therapy in HIV-infected individuals without any severe toxicity. Adverse events observed in HIV/HCV-coinfected participants receiving treatment with PEG INF and ribavirin were similar to those occurring in HCV-monoinfected participants. Drug interactions between antiretrovirals and treatment for hepatitis C concern mostly ribavirin and reverse transcriptase inhibitors (Mallolas and Laguno 2008).

12.1.4 Potential for Adverse Effects from Leukapheresis

Risks associated with leukapheresis are similar to those seen with whole blood transfusions. They rarely include infection (<1% of persons) and commonly include nausea, fainting, dizziness, bruising at the needle puncture site, blood loss, and a transient decrease in platelet or red blood cell counts in 10% to 25% of persons. Potential problems of a leukapheresis procedure when citrate is given intravenously as an anticoagulant rarely includes seizures in <1% of persons and commonly includes muscle cramping, numbness, chilling, tingling sensations, and feelings of anxiety. Citrate is approved by the Food and Drug Administration for this use. If citrate/heparin or heparin alone is used as the anticoagulant, there may be a transient increase in clotting time, which may lead to blood loss in very rare instances (<1%). There is also a small risk of technical problems with the apheresis machine (1:1000 phereses).

12.1.5 Risks of Phlebotomy

The primary risks of phlebotomy include occasional bleeding or bruising of the skin at the site of needle puncture, and the sensation of transient lightheadedness or rarely, fainting or infection. The amount of blood drawn for research purposes shall not exceed 10.5 mL/kg or 550 mL, whichever is smaller, over any 8-week period.

12.2 Human Subject Protections

Participants will be fully counseled prior to entry into the study as to the potential risks of the study. Participants who, in the opinion of the study team, do not fully comprehend these potential risks will not routinely be offered participation in the study. Participants will be monitored closely during their participation in the study, and informed of any new information regarding the study treatment that may influence their willingness to continue study participation.

13 Study Recruitment

The study will be advertised and posted on the NIH web site. The University of Pittsburgh AIDS Clinical Trials Unit will recruit participants from its Volunteer Registry. IRB-approved recruitment materials will be distributed among AIDS service organizations and other HIV providers in the region. Both the NIH and the University of Pittsburgh have recently completed drug intensification studies and have been successful in enrolling participants willing to complete the frequent visits.

In the most recent study, we used the current viral RNA enrollment criterion (≥ 0.38 copies/mL) to study raltegravir intensification; 36 participants were screened for the study and 10 were eligible; the remainder were excluded chiefly on the basis of viral RNA levels. Nevertheless, 9 of the 10 enrolled participants completed this study and had evaluable data that were useful in determining whether viremia decreased. To improve our statistical analysis, we have increased the sensitivity of the assay (lower limit of quantification = 0.1 copies/ml) and will use 0.1 copies/ml as cutoff.

13.1 Gender, Ethnicity, and Race Consideration

Participants will not be excluded based on race, gender, or ethnicity. It is hoped that the racial and ethnic character of the participants in this study will reflect, as closely as possible, the demographics of the HIV epidemic in the United States. The NIAID has an outreach program to medically underserved minority participants in order to improve their access to clinical trials. The University of Pittsburgh's AIDS Clinical Trials Unit makes a concerted effort to provide access to AIDS clinical trials for women and minorities.

13.2 Children and Pregnant Women

This study will be limited to adults 18 years of age and older. Insufficient data are available to evaluate the safety and efficacy of pegylated interferon in the pediatric population. In addition, this study is a no benefit study and would not be applicable to pediatric populations. The risks of pegylated interferon alpha 2b treatment during pregnancy have not been evaluated. Therefore, pregnant or nursing women will be excluded from this study. Any woman of childbearing potential must have a negative pregnancy test at screening, baseline, and prior to each dose of pegylated interferon and also agree to use two accepted methods of contraception throughout the study.

14 Benefits/Compensation/Alternatives

Financial compensation will be provided to study participants as outlined below. Participants will receive remuneration for the immediate costs associated with their study-related expenses like travel expenses, lodging, etc., as provided by the National Institutes of Health.

Participants will be financially compensated according to the NIH Normal Volunteer Guidelines proportionate to the inconvenience of the procedures necessary to obtain the samples. The compensation schedule is as follows:

Day 0 to Week 24: \$40 at each visit
Leukapheresis: \$100 each

The University of Pittsburgh AIDS Clinical Trials Unit will provide compensation for travel based on zip code and distance from the University.

This is a no benefit study; the alternative is not to participate. By participating in this study, participants may contribute to our understanding of persistent HIV viremia in individuals receiving potent antiretroviral therapy.

15 Evaluation of Safety

All enrolled participants who have received any study drugs will be evaluated for safety. Safety will be assessed by physical examination, vital signs, hematology, chemistry, urinalysis, and assessment of AEs. The severity of signs, symptoms, and AEs will be determined by using the Toxicity Severity Scale (Appendix 2).

Recording/Documentation

At each contact with the subject, information regarding adverse events will be elicited by appropriate questioning and examinations. All events, both expected/unexpected and related/unrelated will be recorded on a source document. Source documents will include: progress notes, laboratory reports, consult notes, phone call summaries, survey tools and data collection tools. Source documents will be reviewed in a timely manner by the research team. All reportable adverse events that are identified will be recorded in CRIMSON, or the appropriate case report form (CRF), or source document. The start date, the stop date, the severity of each reportable event, and the PI's judgment of the AEs relationship and expectedness to the study agent/intervention will also be recorded in CRIMSON, or on the appropriate CRF, or source document.

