5.4 Entry (Day 0)

Participants will have laboratory safety assessments performed and receive their first dose of PEG-IFN. Administration of pegylated interferon will be performed by trained personnel. Vital signs will be obtained, concomitant medications documented, and a targeted physical examination will be performed based upon any signs or symptoms that the subject has experienced since the last visit.

Assessments are detailed in Appendix 1 and include:

- Beck Depression Inventory score
- Complete blood count with differential, platelet count
- Serum chemistries (sodium, potassium, chloride, carbon dioxide, creatinine, urea nitrogen, alkaline phosphatase)
- Urine pregnancy test (women of childbearing age) prior to interferon administration
- ALT, Bilirubin
- Creatinine clearance (Cockcroft-Gault method)
- CD4 count
- Single copy assay for HIV-1 RNA
- HIV-1 RNA standard assay
- Interferon level (baseline)
- PBMCs for storage

5.5 Intensification Phase: Visit 1 (Day 7), Visit 2 (Day 14), Visit 3 (Day 21)

Participants will have laboratory safety assessments performed and receive their subsequent doses of PEG-IFN. Vital signs will be obtained and concomitant medications documented. Administration of interferon will be performed by study personnel. Dosing will be based on body weight obtained during initial evaluation. The last PEG-IFN administration will be on Day 21 (Visit 3). A targeted physical examination will be performed based upon any signs or symptoms that the subject has experienced since the last visit. Assessments are detailed in Appendix 1 and include:

- Beck Depression Inventory score
- Complete blood count with differential, platelet count (STAT, prior to interferon administration)
- Serum chemistries (sodium, potassium, chloride, carbon dioxide, creatinine, urea nitrogen, alkaline phosphatase)
- Creatinine clearance (Cockcroft-Gault method)

- Urine pregnancy test (women of childbearing age) prior to drug administration
- ALT, Bilirubin
- Single copy assay of HIV-1 RNA
- HIV-1 RNA standard assay
- Interferon level

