5.11 Window Periods for Study Visits

The following variable scheduling is permitted for study visits:

Days -58 to 14: ± 1 day

Days 21 to 49: ± 2 days

Days 56 to 84: ± 5 days

Weeks 16 to 48: ± 14 days

6 Concomitant Medications

All concomitant medications will be documented at each study visit.

Concomitant administration of immunomodulatory treatments (including steroids, radiation, IL-2, and anti-neoplastic agents) is not allowed during the course of this trial. Other investigational drugs are excluded. No vaccinations are allowed during the study period from 30 days prior to the time of signing consent to the end of the four week interferon therapy period.

7 Study Drug Administration

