7.1 Drugs and Dosing

All participants will receive pegylated interferon alpha 2b at the dose of 1.5 µg/kg subcutaneously every week for 4 doses. Dosing will be determined at Entry, and Visits 1, 2, and 3 based on subject's body weight obtained at the time of enrollment. Administration of study medication will be performed by study personnel. Antiretroviral therapy will be continued throughout the study.

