7.2 Monitoring Parameters

The Schedule of Events is found in Appendix 1. Participants will be closely monitored for clinical and laboratory evidence of adverse events associated with the study drug or medical complications.

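### The Appendix 1 schedule has no pregnancy test at Visit 3 (Day 21), the fourth interferon dose, although Sections 5.5 and 13.2 require one before that dose.

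*Combined protocol and SAP*

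**What the plan says.** The text is consistent about testing before dosing.

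- Section 13.2: any woman of childbearing potential "must have a negative pregnancy test at screening, baseline, and prior to each dose of pegylated interferon".
- Section 5.4 (Day 0, dose 1): "Urine pregnancy test (women of childbearing age) prior to interferon administration".
- Section 5.5 (Visits 1, 2 and 3 on Days 7, 14 and 21; doses 2 to 4): "Urine pregnancy test (women of childbearing age) prior to drug administration". The same section places the final dose at Visit 3, Day 21.
- Section 7.1 confirms the dosing visits: "Dosing will be determined at Entry, and Visits 1, 2, and 3".

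The grid differs. Section 7.2 states: "The Schedule of Events is found in Appendix 1". Sections 5.4 and 5.5 also send the reader there for the details of their assessments. In that grid the interferon administration row is marked at Entry and Visits 1, 2 and 3. The pregnancy row is marked at Pre-entry 1, Entry, Visit 1 and Visit 2, and nowhere else.

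**The concern.** The schedule table is what clinic staff usually work from at a visit, and this protocol points them to it. At Visit 3 it tells them to give interferon and does not tell them to test for pregnancy first.

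The pre-dose test is the planned means of detecting a pregnancy before further exposure. Section 13.2 says the drug's risks in pregnancy have not been evaluated and describes the study as offering no benefit to participants. Section 8.3 (item 5) makes pregnancy a reason to stop study drug. A missed test would also be a protocol deviation under the definition in Section 15.1.1.

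The blank at the Screen column is not part of this point. Section 13.2 mentions a test at screening, and the Pre-entry 1 test can reasonably serve as that test.

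**Working it through.** The plan gives no numerical figure to reproduce here. The check compares the text with the grid visit by visit, then works out the gap that the missing mark would leave.

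**1. Dosing visits against test marks**

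| Dose | Visit (day) | Test required by text | Interferon marked in Appendix 1 | Test marked in Appendix 1 |
|---|---|---|---|---|
| 1 | Entry (0) | Yes: 5.4, 13.2 | Yes | Yes |
| 2 | Visit 1 (7) | Yes: 5.5, 13.2 | Yes | Yes |
| 3 | Visit 2 (14) | Yes: 5.5, 13.2 | Yes | Yes |
| 4 | Visit 3 (21) | Yes: 5.5, 13.2 | Yes | **No** |

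The grid covers 3 of 4 doses, where the text requires 4 of 4.

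**2. Could the row be misaligned?** The header has 18 columns including the label column. The pregnancy and interferon administration rows each have 18 fields, so there is no sign of a shift. As a further check, the interferon level row falls at Entry and Visits 1 to 4, exactly as Section 9.3 states. The CD4 row falls at Pre-entry 1, Entry, Visits 4, 8 and 9 and the final visit, which matches the visit lists in Sections 5.2 to 5.10. Section 9.5 also names Visit 1 for CD4, and the grid does not show it.

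**3. How isolated is the blank within Section 5.5's list?** The section bullets nine assessments: depression score, blood count, chemistries, creatinine clearance, pregnancy test, ALT/bilirubin, single copy assay, standard HIV RNA and interferon level. Over three visits that is 9 × 3 = 27 cells. Of these, 26 are marked. The one blank is the pregnancy test at Visit 3.

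**4. Interval from the last scheduled test to dose 4 if only the grid is followed.** Section 5.11 allows ± 1 day for visits up to Day 14. For Visit 3 it gives "Days 21 to 49: ± 2 days".

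- Nominal: 21 − 14 = 7 days
- Shortest: (21 − 2) − (14 + 1) = 19 − 15 = 4 days
- Longest: (21 + 2) − (14 − 1) = 23 − 13 = 10 days

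**5. After correction.** With a mark at Visit 3, the pregnancy row reads Pre-entry 1, Entry, 1, 2 and 3, and all 4 doses are covered.

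**The case against.** The strongest reply is that the safeguard exists. Two body sections require the test before the fourth dose and nothing exempts it, so a site that reads Section 5.5 for that visit will do the test. The harm arises only if staff follow the grid and overlook the text. That is correct and limits the weight of the point. It does not remove it, because the protocol itself names the grid as the schedule.

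Second, the table was read from a PDF, and a single mark could have been lost in reading. A full field count rules out a shifted row but not a dropped mark. This stands as a caveat. The agreement of neighbouring rows with the text makes a lost mark unlikely, and the sponsor can settle it by looking at the source table.

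Third, the count of 26 out of 27 covers only the bulleted items. Section 5.5's prose also calls for vital signs, concomitant medications and a symptom-directed examination. Adding these gives 36 cells, of which 32 are marked: the concomitant medication row is blank at all three visits. The grid also lacks creatinine clearance at Visits 6 to 9 (Section 5.7) and the targeted examination at Visit 4 (Section 5.6). So the grid is looser than the text in other places too. That argues for a wider reconciliation and leaves the pregnancy-test gap as it is.

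Finally, no endpoint, analysis, sample size or eligibility rule is touched. That is true, and this point does not claim otherwise.

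**Conclusion.** The concern holds. Appendix 1 contradicts Sections 5.5 and 13.2 at the fourth dose, and the text makes clear which is right: the test is required and the grid omits it.

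The error is one cell. If the grid alone were followed, 1 of 4 doses would lack its test, with the previous test 4 to 10 days earlier. It concerns only women of childbearing potential among 10 participants. They would still have tests at Pre-entry 1 and on Days 0, 7 and 14, and would be under a contraception requirement. It should be corrected because it is a safety check on an unevaluated risk, but the practical harm is small.

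The conclusion assumes that the blank cell is in the source table. The interval also assumes that visits stay within the Section 5.11 windows.

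**What to change.** Mark the pregnancy row at Visit 3 (Day 21) in Appendix 1, so that every visit marked for interferon administration is also marked for the test. Optionally, change the word for the first test in Section 13.2 from screening to pre-entry, to match where it is scheduled. The cost is one table cell: the visit is already scheduled and the text already requires the urine test there.

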15.1 Protocol-specific Adverse Events

15.1.1 Definitions of Adverse Events

Adverse Event: Any untoward or unfavorable medical occurrence in a human subject, that includes any abnormal sign (e.g. abnormal physical exam or laboratory finding), symptom, or disease, temporally associated with the subject's participation in the research, whether or not considered related to the research.

Serious adverse event: Any adverse event that

- results in death;
- is life-threatening (places the subject at immediate risk of death from the event as it occurred);
- results in inpatient hospitalization or prolongation of existing hospitalization;
- results in a persistent or significant incapacity;
- results in a congenital anomaly/birth defect; or
- based upon appropriate medical judgment, may jeopardize the subject's health and may require medical or surgical intervention to prevent one of the other outcomes listed in this definition. *(examples of such events include allergic bronchospasm requiring intensive treatment in the emergency room or at home, blood dyscrasias or convulsions that do not result in inpatient hospitalization, or the development of drug dependency or drug abuse)*

Protocol Deviation: Any change, divergence, or departure from the IRB approved study procedures in a research protocol. Protocol deviations are designated as serious or non-serious and further characterized as

1. Those that occur because a member of the research team deviates from the protocol.
2. Those that are identified before they occur, but cannot be prevented.
3. Those that are discovered after they occur

Serious Protocol Deviation: A deviation that meets the definition of a Serious Adverse Event or compromises the safety, welfare or rights of subjects or others.

Non-compliance: The failure to comply with applicable NIH HRPP policies, IRB requirements, or regulatory requirements for the protection of human subjects. Non-compliance is further characterized as

1. Serious: Non-compliance that
 - a. Increases risks, or causes harm, to participants
 - b. Decreases potential benefits to participants
 - c. Compromises the integrity of the NIH-HRPP
 - d. Invalidates the study data
2. Continuing: Non-compliance that is recurring
3. Minor: Non-compliance that, is neither serious nor continuing.

Unanticipated Problem (UP): Any incident, experience, or outcome that meets all three of the following criteria would be considered a serious UP:

1. unexpected in terms of nature, severity, or frequency in relation to
 - a. the research risks that are described in the IRB-approved research protocol and informed consent document; Investigator's Brochure or other study documents; and
 - b. the characteristics of the subject population being studied
2. related or possibly related to participation in the research
3. suggests that the research places subjects or others at a greater risk of harm (including physical, psychological, economic, or social harm) than was previously known or recognized.

Unanticipated problem that is not an Adverse Event (UPnonAE): An unanticipated problem that does not fit the definition of an adverse event, but which may, in the opinion of the investigator, involve risk to the subject, affect others in the research study, or significantly impact the integrity of research data. These events may involve a greater risk of social or economic harm to subjects or others rather than physical/psychological harm. Such events would be considered a non-serious UP. Examples of a UPnonAE include a breach of confidentiality, accidental destruction of study records, or unaccounted-for study drug.

